Cardiology Department, HNELHD
Clinical Trial Protocol: PRESSURE-AF

Version: 1.4
Date: 24/11/2020

Study Title:	Investigating the Efficacy of Chest Pressure for Direct Current Cardioversion in Atrial Fibrillation: A Randomised Control Trial (Pressure-AF)
Protocol Number:	2020/ETH02116
CTN Number:	ACTRN12620001028998p
Intervention	Chest Pressure
Indication:	Direct Current Cardioversion for Atrial Fibrillation
Study Design:	Investigator-initiated
Version:	1.4
Date:	24th November 2020

CONFIDENTIAL

Cardiology Department, HNELHD
Clinical Trial Protocol: PRESSURE-AF

Version: 1.4
Date: 24/11/2020

PROTOCOL SYNOPSIS

Study Title:	Investigating the Efficacy of Chest Pressure for Direct Current Cardioversion in Atrial Fibrillation: A Randomised Control Trial (Pressure-AF)
Study Period:	2021-2023
Hypothesis	The routine use of manual chest pressure for direct current cardioversion in atrial fibrillation will result in decreased energy requirements and will prove safe for patient and proceduralist.
Objectives:	
Primary objective:
 
• To assess the efficacy of chest pressure for direct current cardioversion in atrial fibrillation. 
The secondary objectives are:
 
• To confirm safety and tolerability of chest pressure for patient and proceduralist
Study Plan	
This is a multi-centre, randomised, single blinded trial of chest pressure for direct current cardioversion in atrial fibrillation.
 
Participants will be screened from all participants referred for cardioversion for atrial fibrillation aged over 18 years of age. Randomisation will occur after consent is obtained and on enrolment into the study.
 
Participants will be randomised to an initial strategy of chest pressure (intervention) or a strategy of chest pressure only if refractory to cardioversion without pressure (control).

Number of participants:	
It is planned that 308 participants will be randomised in a 1:1 ratio to one of two treatment arms:
 
• 154 will undergo standard direct current cardioversion.
➤ 1 shock – 150 Joules without chest pressure➤ 1 shock – 200 Joules without chest pressure➤ 1 shock – 360 joules without chest pressure➤ 1 shock – 360 joules with chest pressure• 154 will undergo an initial strategy of chest pressure.
➤ 1 shock – 150 Joules with chest pressure➤ 1 shock – 200 Joules with chest pressure➤ 1 shock – 360 Joules with chest pressure➤ 1 shock – 360 joules with chest pressure
Key inclusion	Participants who:

CONFIDENTIAL

Cardiology Department, HNELHD
Clinical Trial Protocol: PRESSURE-AF

Version: 1.4
Date: 24/11/2020

- criteria:
- Aged over 18 years of age.
 - Have Atrial Fibrillation.
 - Are referred for direct current cardioversion for atrial fibrillation.
 - Three weeks of therapeutic anti-coagulation prior to cardioversion or transoesophageal echocardiography excluding left atrial appendage thrombus.
- Key exclusion criteria:
- Participants with:
- Pregnant or breastfeeding females.
 - Inability to provide informed consent.
 - Other atrial tachyarrhythmias (atrial flutter or multifocal atrial tachycardia)
 - Medical comorbidity where anticoagulation is contra-indicated
- Test strategy:
- Direct current cardioversion for atrial fibrillation with and without chest pressure as the initial strategy.
- Duration of study per participant:
- Day of procedure only.
- Criteria for evaluation:
- Primary efficacy endpoints
- Total joules provided during encounter.
- Secondary efficacy endpoints:
- Success of first shock for reversion to sinus rhythm.
 - Transthoracic impedance at the time of shock.
 - Sinus rhythm at post cardioversion ECG
- Safety and Tolerability Endpoints
- Patient chest pain post cardioversion (Ordinal Scale 0-10).
 - Incidence of shock provided to proceduralist.
- Statistical methods and analyses:
- Analysis Sets
- Full analysis set (FAS) Intention to Treat (ITT) Protocol: All participants randomised into the study. Participants will be analysed according to the intervention to which they were randomised. Efficacy analyses performed in the FAS are considered supportive of analyses performed in the PP set.
 - Per-protocol (PP) set: All participants from the ITT population who completed the study in compliance with the protocol and who reported no major violation of the study protocol. Participants will be analysed according to the intervention which they received. The final decision to exclude a participant from the PP set will be taken during a blinded data

CONFIDENTIAL

review meeting before database lock. Efficacy analyses performed in the PP set are considered supportive of analyses performed in the ITT set.

Sample Size

A retrospective review of 12 months of direct current cardioversions was performed at our centre. The mean energy provided during an encounter was 280 ± 188 Joules. Assuming a mean reduction of 60 joules in energy in the intervention group (one third of the standard deviation), a total of 308 patients (154 in each arm) would need to be recruited for an alpha of 0.05 and power of 0.8. This has been discussed and confirmed with statisticians at the Hunter Medical Research Institute.

Statistical Analyses

Continuous variables will be reported as mean \pm standard deviation or as median and percentiles if appropriate. Normally distributed variables will be compared using the paired Student's t-test. Otherwise comparisons between both the groups will be performed using the Mann-Whitney U test. Categorical variables will be stated as absolute and relative frequencies and compared using the χ^2 test. All tests are two-tailed. A P-value of <0.05 will be considered as statistically significant.

Sensitivity analyses of the primary endpoint will be performed in the FAS to assess the impact of missing data on the robustness of the primary analysis. The primary analysis will also be repeated in the PP set.

The following secondary endpoints will be analysed and summarised using the methods described for the primary endpoint:

- Success of first shock for reversion to sinus rhythm.
- Average transthoracic impedance.
- Chest pain post procedure – ordinal 0-10 scale.
- Shock provided to the provider.

Successful cardioversion is defined as sinus rhythm 1 minute after cardioversion.

Cardiology Department, HNELHD
Clinical Trial Protocol: PRESSURE-AF

Version: 1.4
Date: 24/11/2020

Table of Contents

PROTOCOL SYNOPSIS	2
LIST OF ACRONYMS AND ABBREVIATIONS	8
1. BACKGROUND AND RATIONALE	11
1.1. ATRIAL FIBRILLATION AND DIRECT CURRENT CARIOVERSION	11
1.2. CLINICAL STUDIES OF DIRECT CURRENT CARIOVERSION FOR ATRIAL FIBRILLATION.....	11

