1.2.2. Efficacy

A retrospective review of 12 months of cardioversions for atrial fibrillation at our centre was performed, with a total of 147 patients. The success of the first and last shocks for reversion of sinus rhythm were 71% and 87% respectively.

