2.7. STUDY TREATMENTS

2.7.1. Description of the control arm

Patients in the control arm will receive sequential shocks of 150J without pressure, 200J without pressure, 360J without pressure and 360J with chest pressure until cardioversion success or four shocks have been provided. The cardioversion will be performed under intravenous sedation guided by an anaesthetist (Propofol ± midazolam weight-based dosing and titrated to effect).

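### The 188 J planning SD comes from an undescribed shock practice; with the protocol's own success rates on the trial's fixed schedule, the stated 80% power for 60 J is not supported

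*Protocol*

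**What the plan says.** The Sample Size section of the synopsis takes its variability from a 12-month review of cardioversions at the centre: "The mean energy provided during an encounter was 280 ± 188 Joules". The effect is given as follows: "Assuming a mean reduction of 60 joules in energy in the intervention group (one third of the standard deviation"). From these it concludes that "a total of 308 patients (154 in each arm) would need to be recruited for an alpha of 0.05 and power of 0.8". Testing is two-sided: "All tests are two-tailed. A P-value of <0.05 will be considered as statistically significant".

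Section 1.2.2 describes a 12-month review at the same centre, with 147 patients: "The success of the first and last shocks for reversion of sinus rhythm were 71% and 87% respectively".

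The primary endpoint is total joules. Section 2.7.1 fixes what can be delivered: "Patients in the control arm will receive sequential shocks of 150J without pressure, 200J without pressure, 360J without pressure and 360J with chest pressure", stopping at success or after four shocks. Section 2.7.2 sets the same four energies for the pressure arm. The protocol does not say which energies, or how many shocks, lie behind the 188 J. Nor does it say that the figure was adapted to this schedule.

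**The concern.** Under the fixed escalation a protocol-compliant total has four possible values, and the last two are far from the first. The SD is therefore set almost entirely by how many patients need a third or fourth shock. An SD observed under another shock practice need not apply. The protocol's own success rates allow a check, and they point to a larger SD than 188 J.

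The SD is the only variability input to the 308. Section 8.1 excludes efficacy outcomes from the 12-month review, and the protocol describes no re-estimation of the SD, so nothing it sets out would reveal a wrong value. If the SD is too small, a null result could be read as evidence against chest pressure from a trial believed to have 80% power.

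**Working it through.** **Inputs.** Difference 60 J, SD 188 J, mean 280 J, two-sided 5%, power 80%, 154 per arm (synopsis, Sample Size). Energies 150, 200, 360 and 360 J (sections 2.7.1 and 2.7.2). First- and last-shock success 71% and 87% (section 1.2.2).

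**1. The plan's own figure.** n per arm = 2 × (1.960 + 0.842)² × (188/60)² = 154.1. The stated 308 reproduces. The formula is sound; the question is the input. (60/188 is 0.319, so one third is a rounding.)

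**2. Possible totals.** 150; 150 + 200 = 350; 350 + 360 = 710; 710 + 360 = 1070 J.

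**3. 71% at 150 J and a mean of 280 J.** For any distribution with 71% at 150 J, the SD is at least (280 − 150) × √(0.71/0.29) = 203 J. On the four permitted values, let a, b and c be the proportions at 350, 710 and 1070 J:

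- a + b + c = 0.29 and 200a + 560b + 920c = 130, so a = 0.09 + c and b = 0.20 − 2c.
- With D the excess over 150 J, the mean of D² is 40,000a + 313,600b + 846,400c = 66,320 + 259,200c, which is smallest at c = 0.
- Minimum SD = √(66,320 − 130²) = √49,420 = 222 J, from a split of 71/9/20/0%.

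**4. Adding 87% final success after four shocks.** The 13% not converted have received all four shocks, so at least 13% sit at 1070 J. The smallest SD has the other 16% converted at shock 2:

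- Mean = 150 + 200 × 0.16 + 920 × 0.13 = 301.6 J, so 280 J is not attainable either.
- SD = √(40,000 × 0.16 + 846,400 × 0.13 − 151.6²) = √93,449 = 306 J.
- If all later successes came at shock 4, the mean and the SD would both be about 417 J.

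**5. What 188 J would need.** Keep 71% at 150 J but drop the 280 J mean and the 87%. Putting everyone else at 350 or 1070 J, 4% at 1070 J gives an SD of 191 J and 3.8% gives 187 J. So about 4% or fewer may reach 1070 J.

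**6. A milder assumption.** A split of 71/24/0/5% has mean 150 + 48 + 46 = 244 J and SD √(9,600 + 42,320 − 94²) = √43,084 = 208 J.

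**7. Power for 60 J at 154 per arm.** Common SD, two-sample t-test, noncentrality 60 / (SD × √(2/154)). The detectable difference is about 2.802 × SD × √(2/154); the t-based values shown are within 1 J of this.

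| Case | SD (J) | Power for 60 J | Detectable at 80% (J) |
|---|---|---|---|
| As planned | 188 | 80% | 60 |
| 71% first shock, 5% at 1070 J, none at 710 J | 208 | 71% | 67 |
| 71% first shock, mean 280 J (minimum SD) | 222 | 66% | 71 |
| 71% and 87% (minimum SD) | 306 | 40% | 98 |
| 71% and 87% (maximum SD) | 417 | 24% | 134 |

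**8. Unequal SDs.** An effective intervention may shrink the pressure arm's SD. With a control SD of 306 J and a pressure-arm SD of zero, the root-mean-square SD is 306/√2 = 216 J, still above 188 J, and power is 68%. With a control SD of 208 J, 80% power is reached once the pressure-arm SD is at or below about √(2 × 188² − 208²) = 166 J.

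**The case against.** The strongest reply is that this joins figures which the protocol never places under one shock practice. The mean, the 71% and the 87% are historical, and the two review descriptions are not expressly the same dataset. The schedule is prospective. The 87% is success of the last shock in past practice; the protocol does not say that those patients had four shocks, reached 360 J twice, or had pressure on the final one. Some past failures might convert under the full escalation.

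That stands. A reader might infer that 188 J is impossible under this schedule, or that the trial has 40% power. The documents support neither. With 71% at 150 J, a split of 71/24/2/3% has mean 237 J and SD 184 J. If first-shock success at 150 J were lower, a split of 55/35/9/1% has mean 280 J and SD 184 J. The 188 J may also be quite right for past practice.

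The reply does not restore the stated power. If the review's success rates do not transfer, its SD has no better claim to. Each attainable split above sets aside a figure the protocol reports: the first drops the 280 J mean and the 87%, the second the 71% and the 87%.

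A second reply is that the power figures concern a comparison of means, whereas the plan switches to the Mann-Whitney test for non-normal data, which is likely with four skewed values. This also stands, but it does not rescue the 80%. Mann-Whitney power is not set by a mean difference. With control 71/16/0/13%, two pressure-arm patterns with the same 60 J reduction gave about 7% (71/24.3/0/4.7%) and 98% (90/0/0/10%) in simulation (4,000 runs each).

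**Conclusion.** The concern holds as a point about an unsupported planning assumption; the calculation itself has no error. The 308 follows from its inputs, but the SD behind it has not been shown to apply to the trial's schedule, and the protocol's own figures point to a larger one.

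The size depends on what carries over. If the 71% applies at 150 J and the mean is 280 J, power for 60 J is at most about 66% with a common SD. If the 87% also applies after four shocks, it is at most about 40% with a common SD, and at most 68% even with no variation in the pressure arm. With 5% at 1070 J and none at 710 J it is about 71%, and above 80% if the pressure arm's SD falls below about 166 J. All of this is for a comparison of means. It should be fixed, but it does not invalidate the design.

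**What to change.** In the Sample Size section:

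- State the shock energies, and the maximum number of shocks, behind the 280 ± 188 J.
- Derive the control and pressure-arm mean and SD from the totals 150, 350, 710 and 1070 J, with stated success rates per shock in each arm. Use the review data where they can be mapped. A patient converted at a higher first energy has no observed outcome at 150 J, so some rates may have to be stated as assumptions.
- Restate the power for 60 J at 308 participants, or the difference detectable with 80% power, as a range over those rates and for the test that will be used.

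The cost is a short re-analysis of data already held and a revised paragraph, probably with a less favourable power figure. The sample size, endpoint and shock schedule are untouched.

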2.7.2. Description of intervention arm

Patients in the intervention arm will receive sequential shocks of 150J with pressure, 200J with pressure and two shocks at 360J with pressure until cardioversion success or four shocks have been provided. The cardioversion will be performed under intravenous sedation guided by an anaesthetist (Propofol ± midazolam weight-based dosing and titrated to effect).

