3.2. DAY OF CARDIOVERSION

On the day of cardioversion the following will be performed:

- Review eligibility criteria.
- Record participant medical history and medications.
- Record the height and weight of the patient.
- Vital signs (see Section 5.2).
- 12-lead ECG.
- Written informed consent.
- Upon confirmation of eligibility and consent to proceed, participants will be randomised.

The protocol for DC cardioversion (control or intervention) will then be performed based on randomisation. After the DC cardioversion is completed, the following will be performed:

- Chest pain 30 minutes post procedure will be recorded (0-10 ordinal scale)
- Record of post-procedural complications:
 - shock provided to proceduralist

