8.2. STATICAL ANALYSIS PLAN

Continuous variables will be reported as mean \pm standard deviation or as median and percentiles if appropriate. Normally distributed variables will be compared using the paired Student's t-test. Otherwise comparisons between both the groups will be performed using the Mann–Whitney U test. Categorical variables will be stated as absolute and relative frequencies and compared using the χ^2 test. All tests are two-tailed. A P-value of <0.05 will be considered as statistically significant.

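### The generic test rule in practice sends four-valued total joules to Mann-Whitney, while the 308 patients and 80% power were derived for a 60 J difference in means

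*Protocol*

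**What the plan says.** The primary endpoint is "Total joules provided during encounter" (Protocol synopsis; Section 4.1.1 is equivalent). Control patients receive "sequential shocks of 150J without pressure, 200J without pressure, 360J without pressure and 360J with chest pressure until cardioversion success" or four shocks (Section 2.7.1). Intervention patients receive "150J with pressure, 200J with pressure and two shocks at 360J with pressure until cardioversion success or four shocks have been provided" (Section 2.7.2). The energy steps are therefore the same in both arms.

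The sizing paragraph of the synopsis starts from a retrospective review: "The mean energy provided during an encounter was 280 ± 188 Joules". It continues "Assuming a mean reduction of 60 joules in energy in the intervention group" and arrives at 154 per arm for alpha 0.05 and power 0.8.

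The only test rule is generic and appears twice. Normally distributed variables get a paired Student's t-test; for the rest, "Otherwise comparisons between both the groups will be performed using the Mann-Whitney U test" (synopsis, Statistical Analyses). Section 8.2 repeats this: "Otherwise comparisons between both the groups will be performed using the" same rank test. Neither place says how normality is judged or names a test for total joules specifically.

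On baseline data, Section 3.2 lists "Record the height and weight of the patient" as well as medical history and medications. Section 8.4 uses BMI, left atrial size, age and anti-arrhythmic therapy for further analyses. No adjustment of the primary comparison is described.

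**The concern.** The sample size makes a promise about one quantity and the test rule examines another. The trial was sized to detect a change in average energy, and its hypothesis is that pressure lowers energy requirements. Mann-Whitney asks whether a patient in one arm tends to rank below a patient in the other. With most patients tied at the lowest total, that ranking is driven largely by first-shock success and takes no account of how many joules separate the steps.

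Two things are at stake. The stated power does not belong to the test that will be run. The p-value that decides the trial can also disagree with the difference in joules that readers will quote beside it. In addition, the t-test branch specifies a paired test although patients are randomised 1:1 to two independent arms and no pairing is described.

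**Working it through.** **1. Reproduce the plan's figure.** Inputs (synopsis): difference 60 J, SD 188 J, two-sided alpha 0.05, power 0.80, 1:1 allocation.

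n per arm = 2 × (1.960 + 0.842)² × 188² / 60² = 154.1.

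Power at 154 per arm is 0.80. The exact two-sample t calculation gives 155.1 per arm, and power 0.797 at 154. So 308 is a comparison of two independent means, with no allowance for a rank test.

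**2. Values the endpoint can take.** Cumulating the ladder: 150; 150 + 200 = 350; 350 + 360 = 710; 710 + 360 = 1070 J. There are no other compliant totals. Section 1.2.2 reports 71% first-shock success historically, so about 71% of control patients would sit at 150 J if that rate holds.

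**3. Which branch applies.** In simulated control arms of 154 drawn from these four values, under several assumed splits, a Shapiro-Wilk test rejected normality in all 300 arms checked per scenario. The rule therefore leads to Mann-Whitney.

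**4. What that test examines.** Its target is θ = P(intervention total lower) + 0.5 × P(tie), with θ = 0.5 under no effect. The mean difference is not an input.

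**5. Power for the same true 60 J reduction.** Assumed control split at 150/350/710/1070 J: 71/11/5/13%. The 71% and the 13% follow the historical 71% first-shock and 87% final success. The 11/5 division, and having no one convert only at the fourth shock, are assumptions.

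Mean = 0.71×150 + 0.11×350 + 0.05×710 + 0.13×1070 = 319.6 J. Mean of squares = 203,492, so SD = √(203,492 − 319.6²) = 318 J.

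Simulation at 154 per arm, Welch t against tie-corrected Mann-Whitney (repeat runs agree to about one percentage point):

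| Where the 60 J comes from | Intervention split (%) | θ | Mean comparison | Mann-Whitney |
|---|---|---|---|---|
| Failure cut equally at shocks 1–3 (each × 0.791) | 77.1/11.7/4.8/6.4 | 0.536 | 45% | 29% |
| First-shock failure only (29% to 18.7%) | 81.3/7.1/3.2/8.4 | 0.551 | 44% | 56% |
| Later shocks only | 71/20.7/2.3/6 | 0.514 | 47% | 8% |

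With no effect, both tests reject in about 5% of trials, so the mean comparison holds its level on these skewed data at this sample size.

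**6. Separate the test from the SD.** With an SD of 318 J in both arms, the normal approximation gives 60 / (318 × √(2/154)) = 1.66 and power of about 38%. The scenarios above do a little better because the intervention SD is smaller (233 to 268 J). So the mean comparison's fall from 80% is an SD effect. Holding the control arm at the protocol's own mean 280 J and SD 188 J isolates the choice of test:

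- Control 58.4/28.5/13.0/0%, with 60/560 = 10.7% of patients moved from 710 to 150 J: mean comparison 93%, Mann-Whitney 71%.
- Control 53.8/37.8/6.4/2.0%, with 60/200 = 30% moved from 350 to 150 J: mean comparison 79%, Mann-Whitney above 99%.

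**7. Can the two measures point in different directions?** Yes, under an assumed pattern. Control 71/10/4/15% has mean 330.4 J and intervention 66/20/7/7% has mean 293.6 J, a fall of 36.8 J. Yet θ = 0.491, slightly favouring control.

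**The case against.** The best defence is that Mann-Whitney is valid here, keeps its 5% level, and is the more powerful choice when the benefit is confined to the first shock (56% vs 44%). That is a plausible mechanism, so moving to means is a trade-off. This stands. A reader might infer that the rank test throws power away; the figures do not support that as a general statement.

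The extreme rows should not be over-read. The 47% vs 8% case supposes that pressure does nothing at shock 1 yet greatly improves shock 2. Section 1.3 argues that pressure lowers transthoracic resistance, which gives no reason to expect that pattern. It shows how far the tests can part, not what is likely.

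A reader might also infer that the choice of test explains why none of the mean-comparison figures in the main table reach 80%. It does not: the SD implied by the assumed split does.

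That the rule must always select Mann-Whitney is a near-certain inference, not something written: no normality criterion is given. Encounters that depart from the ladder could add other totals but would not make them normal.

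Joules will be described in any case, because Section 8.5 requires means, medians and SDs by group. That softens the complaint but does not align the deciding test with the sized quantity.

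Finally, it is tempting to call the absence of covariate adjustment an error. The documents do not support that. An unadjusted randomised comparison is valid, adjustment may sit in a statistical analysis plan that is not shown, and Section 8.4 does use these variables.

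**Conclusion.** The point holds as a mismatch inside the protocol: the sizing target and the test rule are both stated, and they concern different quantities. The 80% power belongs to a comparison of means. For the same true 60 J, Mann-Whitney power ran from 8% to 56% on the 71/11/5/13% split, and from 71% to above 99% on splits matching the protocol's own mean and SD. The direction and size of the discrepancy depend on which shocks improve, which the documents cannot settle.

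The conclusion rests on compliant encounters following the ladder. The power figures also rest on the assumed splits of later-shock outcomes. The paired t-test is a plain misstatement for two independent arms and needs no assumption. Whether 188 J is a credible SD for this ladder is a separate question that changing the test does not solve.

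**What to change.** Take the primary endpoint out of the normality rule and name one analysis: the difference in mean total joules with a 95% CI in the ITT FAS, unpaired, by Welch's method or by linear regression with robust standard errors. State Mann-Whitney as a sensitivity analysis. Replace the paired t-test with an unpaired one wherever the generic rule remains, in both the synopsis and Section 8.2.

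The cost is wording only, with no extra patients or data. The downside is some loss of power if the benefit is confined to the first shock (44% vs 56% in the scenario above).

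As an optional efficiency gain, and not the correction of an error, pre-specify adjustment for BMI, age, anti-arrhythmic therapy and site. Height, weight and medications are already recorded before the shock. The size of the gain is unknown because the documents give no R-squared.

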1.3. STUDY RATIONALE

The success of direct current cardioversion relies on the delivery of energy to the heart. Most of the energy is displaced laterally across the chest wall, with only a small proportion delivered to the heart. (2) Chest pressure reduces transthoracic resistance by 25%, increasing cardiac energy delivery. (3) Therefore, routine chest compression may improve the success rate and decrease overall energy use.

Biphasic energy will be utilised due to reported increased efficacy and less myocardial stunning compared to monophasic cardioversion. (4, 5) Three weeks of therapeutic anticoagulation will be required prior to cardioversion in keeping with international guidelines or transoesophageal echocardiography excluding left atrial appendage thrombus. (6) 150 joules shall be used as the initial energy given guideline recommendations for starting energies between 100 and 200 joules. (7, 8) Cardioversion will be timed to end-expiration to maximally reduce transthoracic impedance. (9)

Cardiology Department, HNELHD
Clinical Trial Protocol: PRESSURE-AF

Version: 1.4
Date: 24/11/2020

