4.1.2. Secondary

- First shock success in reversion to sinus rhythm
- Transthoracic impedance at the time of shock
- Sinus rhythm at post cardioversion ECG

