5. TRIAL MEASUREMENTS

5.1. EFFICACY

Total joules provided during a patient encounter will be measured. First shock success percentage will be compared between groups. Transthoracic impedance with each shock (a measurement provided by the defibrillator) will also be recorded.

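### The secondary impedance endpoint is not tied to a shock; if its average runs over a patient's shocks, refractory controls contribute a pressured reading

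*Protocol*

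**What the plan says.** The synopsis (criteria for evaluation) and section 4.1.2 both name the secondary endpoint as "Transthoracic impedance at the time of shock". Neither says which shock. Section 5.1 adds: "Transthoracic impedance with each shock (a measurement provided by the defibrillator) will also be recorded". The synopsis list of secondary endpoints under Statistical Analyses calls the variable "Average transthoracic impedance" and applies the methods of the primary endpoint to it. Section 8 does not define it.

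The arms differ in which shocks carry pressure. Under section 2.7.1 controls receive "150J without pressure, 200J without pressure, 360J without pressure and 360J with chest pressure until cardioversion success or four shocks have been provided". Under section 2.7.2 the intervention arm receives "150J with pressure, 200J with pressure and two shocks at 360J with pressure until cardioversion success or four shocks have been provided". A patient therefore has between one and four readings, and the count is fixed by when cardioversion succeeds.

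The mechanism is stated in section 1.3: "Chest pressure reduces transthoracic resistance by 25%, increasing cardiac energy delivery". The only information on how many patients need further shocks is the local review in section 1.2.2: "The success of the first and last shocks for reversion of sinus rhythm were 71% and 87% respectively".

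**The concern.** At least three variables fit the text: the first-shock reading, a within-patient average, and an average over all shocks pooled. They do not estimate the same thing.

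Averaging over shocks raises two problems in this design. First, a control's fourth shock is given with pressure, so the value for the most refractory controls contains the condition they are meant to be compared against. Second, shocks stop at success, and the trial expects pressure to change success. The number of readings is therefore an outcome of treatment, and the arms are averaged over differently selected shocks.

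Impedance is in the trial to test the mechanism in section 1.3, which is a contrast of pressure with no pressure. An endpoint with several admissible versions also leaves room to choose among them once the data are seen.

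**Working it through.** **The plan's own figure.** The protocol gives no power or sample size for impedance. Its N of 308 rests on total joules (60 J difference, SD 188 J, two-sided alpha 0.05, power 0.80): n per arm = 2 × (1.960 + 0.842)² × (188/60)² ≈ 154.1, rounded up to 155, or 310 in total. Power at 154 per arm is 0.7997. The stated 308 is reproduced to within rounding, and nothing below bears on it.

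**Inputs**
- Impedance without pressure is set to 1 and with pressure to 0.75 (section 1.3, treating its resistance figure as impedance).
- Controls: shocks one to three without pressure, shock four with it (section 2.7.1). Intervention: every shock with pressure (section 2.7.2).
- Share of controls reaching shock four, q4: not given. Assumed range 0.13 to 0.29, from the local review: 1 − 0.87 = 0.13 failed overall, 1 − 0.71 = 0.29 failed the first shock. The review's shock sequence is not described, so carrying these rates over is itself an assumption.
- For steps 1 to 4, all patients share the same underlying impedance and it does not drift from shock to shock.

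**1. First shock only.** Control 1.00, intervention 0.75; contrast 25.0 points. Every shocked patient contributes one reading under the randomised condition.

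**2. One control who reaches shock four.** Average = (3 × 1 + 0.75)/4 = 0.9375, or 6.25% below the unpressured value. Controls who stop earlier are not mixed.

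**3. Within-patient averages, whole arm.** Control mean = 1 − 0.0625 × q4.

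| q4 | Control mean | Contrast with 0.75 (points) | Share of effect lost |
|---|---|---|---|
| 0.13 | 0.992 | 24.2 | 0.0081/0.25 = 3% |
| 0.29 | 0.982 | 23.2 | 0.0181/0.25 = 7% |

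**4. All shocks pooled, mixing only.** Shocks per control = 1 + q2 + q3 + q4, with q2 = 0.29. The share reaching shock three, q3, is also not given and is varied over the same range. Pressured share = q4 divided by shocks per control; control mean = 1 − 0.25 × that share.

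| q3 | q4 | Shocks per control | Pressured share | Control mean |
|---|---|---|---|---|
| 0.29 | 0.13 | 1.71 | 7.6% | 0.981 |
| 0.13 | 0.13 | 1.55 | 8.4% | 0.979 |
| 0.29 | 0.29 | 1.87 | 15.5% | 0.961 |

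Mixing alone would cost about 8–16% of the contrast.

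**5. Pooled, with selection.** Step 4 leaves selection out. With N shocks per patient and patient average Z, the pooled mean is E(NZ)/E(N) = E(Z) + Cov(N, Z)/E(N). If high impedance makes failure more likely, the covariance term tends to be positive. It will tend to be larger in controls if they need more shocks, which raises the control mean and widens the contrast. This works against the mixing.

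An illustrative simulation assumed a coefficient of variation of 25% for impedance, 71% first-shock success in controls and logistic dependence of success on log impedance. It gave pooled intervention-to-control ratios of 0.756 with no dependence, 0.742 with moderate and 0.734 with strong dependence, against a true 0.750. The last two exaggerate the effect. Within-patient averages stayed on the diluted side (0.752–0.763).

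The simulation has less mixing than step 4: 0.75/0.756 = 0.992, so the pressured share is about 0.008/0.25 = 3%. It shows that the sign can reverse, not that it would if 13% or more of controls reach shock four.

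**The case against.** The three descriptions can be read together: one says when the reading is taken, one how often, one how it is summarised. The synopsis reports continuous variables as mean and SD, so the word average may mean only the group mean. This stands in part. The text does not force an average over shocks, and a reader who infers an outright contradiction, or a settled plan to average each patient's readings, goes further than the protocol does. The neighbouring items in the analysis list name patient-level variables, and only impedance, which has repeated readings, carries the word; that favours an average over readings without proving it. On the group-mean reading the choice of shock is still open.

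It may also be said that pressure at shock four belongs to the control strategy, so an average over the encounter parallels total joules. That would be fair for a strategy outcome. But total joules already captures the strategy, and section 1.3 gives impedance a mechanistic role that needs pressured and unpressured readings in comparable patients.

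The size is small and the endpoint secondary. That stands in full, and it sets the weight of the point.

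Lastly, leaving such detail to a statistical analysis plan would be normal. Here, though, the protocol itself gives the variable two different names, and these should agree.

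**Conclusion.** The point holds as a minor one. The protocol does not say which impedance reading is analysed. If the average is within patient, refractory controls carry a pressured reading, and 3–7% of the 25-point contrast is lost. This rests on the protocol's 25% reduction, equal underlying impedance across patients, and an assumed 13–29% of controls reaching shock four.

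Two stronger conclusions might be inferred and are not supported. One is that the bias always runs towards no difference: the mixing does, but under pooling the extra weight on refractory patients can offset or reverse it, so the net direction is uncertain. The other is that 13% is the documented share of controls reaching shock four: it is the overall failure rate in a retrospective series with an unstated sequence. Nothing here suggests that a trial conclusion would change, and the primary endpoint and N = 308 are untouched.

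**What to change.** Use one definition in both synopsis lists and in section 4.1.2: transthoracic impedance at the first shock, compared between the arms as randomised. This reading exists for every shocked patient, precedes any selection by outcome, keeps the full contrast, and matches the first-shock anchor already used for the success endpoint. Report later readings as supportive, by shock number and pressure status; a repeated-measures model with those terms is an acceptable alternative for them.

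The cost is wording only. Section 5.1 already records the reading at each shock, so no new data are needed, and neither the shock sequences nor the sample size change.
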